10.5.6. Interim Reporting

Interim reports may be prepared during the course of the study until the final study outcomes are available. The usual components of this report are:

- patient accrual rate;
- distribution of pretreatment characteristics;
- cryoablation procedure details;
- frequency and severity of the toxicities.

11. DATA MANAGEMENT

11.1. Data Collection

Patient specific data will be collected by the study coordinator. No patient specific data will be released. Deidentified data will be collected using a web-based electronic data capture (EDC) system. The system will be fully validated and compliant with FDA 21 CFR 11 guidance.

Participating sites will enter all patient data collected during the conduct of the protocol into the EDC system using the electronic case report forms (eCRFs) developed for each stage of the study. The system will use dynamic eCRFs to ensure an efficient entry process and completion of all necessary forms based on the individual needs of each enrolled patient.

All sites will receive training on the proper use of the system and the data collection expectations for this protocol. A Galil Medical representative will train each site on how to create a new patient, enter data into the eCRFs, edit/update data on existing eCRFs, resolve queries and approve/sign-off on each form/completed eCRF.

11.2. Data Processing

To help minimize data entry errors, the EDC system will include real-time edit checks that will identify potential data issues at the time of entry. These edit checks will display on-screen messages when triggered so that the investigator or data entry designee can immediately review the potential data issue and address it before leaving the form.

All eCRFs will be reviewed by clinical staff within Galil Medical to check for completeness and potential unresolved data entry issues. A Galil Medical representative will generate queries within the system for open data issues and follow-up with each site, as necessary, to resolve key data element issues.

The investigator will review all eCRFs created and will approve each patient's eCRFs via electronic signature within the EDC system. The database will be subject to periodic interim analyses based on

key study milestones. Prior to each milestone analysis, a Galil Medical representative will work with each site to ensure a data set that is as complete and accurate as possible. At the conclusion of the study, the database will undergo a final review and then be locked. No changes will be allowed in the database after the final lock without the written authorization of the appropriate Galil Medical management team members.

The Institution will be provided a final electronic record of completed, locked Case Report Forms and other written records, accounts, notes and reports relating to the Study. These records will be retained for the period of time required by Applicable Laws.

12. MONITORING PROCEDURES

12.1. Monitoring and Auditing

Participating sites will be managed remotely via regular telephone contact and routine monitoring visits will be conducted. When necessary, site visits will be performed by an authorized representative from Galil Medical, and will be conducted according to the monitoring plan and applicable FDA and GCP guidelines.

In addition, sites may be subject to an audit visit by Galil Medical, the FDA or a local regulatory authority. If such a site audit occurs, the investigator agrees to provide access to all pertinent patient records, eCRFs and other site documents deemed necessary to complete the audit visit.

By signing the Study Agreement, the investigator grants permission to authorized representatives of Galil Medical to conduct on-site monitoring visits for the purpose of reviewing the collected study data and to review site procedures employed in the conduct of this study.

It is important that the investigator(s) and their relevant personnel are available during the monitoring visits and possible audits or inspections and that sufficient time is devoted to the process.

13. SAFETY ASSESSMENTS

All adverse events (AEs), serious adverse events (SAEs) and unanticipated adverse device effects (UADEs) that occur within 30 days after the cryoablation procedure is performed will be recorded. The AEs, SAEs and UADEs identified within the first 30 days after the cryoablation procedure will be followed and reported until resolution.

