5.7. Risks

Potential risks of pulmonary tumor cryoablation in the intra procedure/early post-procedure period include bleeding, cough, hemoptysis, fever, infection, hypertension, pleural effusion, pneumothorax, nerve or skin injury.

Potential delayed risks of pulmonary tumor cryoablation include pneumothorax, pulmonary embolus, infection, and other unlikely complications, including death.

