13.1. List of Definitions

Adverse Event (AE)

Any untoward or unfavorable medical occurrence in a human patient, including any abnormal sign (for example, abnormal physical exam or laboratory finding), symptom, or disease, temporally associated with the patient's participation in the research, whether or not considered related to the patient's participation in the research. All AEs must be recorded in the electronic database. A description of the event, including the start date, resolution date, action taken and the outcome should be provided, along with the investigator's assessment of the relationship between the AE and the study procedures.

The anticipated cryoablation related adverse events and their corresponding Common Terminology Criteria for Adverse Events (CTCAE) Terms are listed in Appendix B.⁴³

Serious Adverse Event (SAE)

Category 4 or higher of the CTCAE guidelines and the following ICH definitions will be used in the protocol as applicable.

- Results in Death

- Is Life Threatening

Note: The term 'life threatening' in the definition of serious refers to an event in which a patient was at immediate risk of death at the time of the event; it does not refer to an event which hypothetically might have caused death if it were more severe.

- Requires inpatient hospitalization or prolonged existing hospitalization

Note: Complications that occur during hospitalization are AEs. If a complication prolongs hospitalization or fulfills any other serious criteria, the event is serious. Hospitalization for elective treatment of a pre-existing condition that did not worsen from baseline is not considered to be an AE.

- Results in persistent or significant disability/incapacity

Note: The term disability means a substantial disruption of a person's ability to conduct normal life functions. This definition is not intended to include experiences of relatively minor medical significance (e.g., uncomplicated headache, nausea, vomiting, diarrhea, influenza, or accidental trauma) that may interfere or prevent everyday life functions, but do not constitute a substantial disruption.

- Results in permanent impairment of a body structure or body function or requires surgical intervention to prevent permanent impairment of a body structure or body function

- Leads to fetal distress, fetal death or a congenital anomaly/birth defect

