13.3. Recording and Reporting SAEs and UADEs

Any SAE must be reported by the investigator by calling the Galil Medical SAE reporting line (listed below) within **24 hours** of learning of the event. The site must maintain adequate documentation of timely event reporting.

At any time the Galil Medical SAE reporting line can be reached at [REDACTED]

Additionally, an email may be sent to [REDACTED] to report a SAE or UADE.

The investigator or designee must forward the requested follow-up information to the Galil Medical clinical representative as the event continues and/or resolves.

Investigators are required to submit to the IRB and Galil Medical a report of any UADE occurring during an investigation as soon as possible, but in no event later than 10 working days after the investigator learns of the effect. The site must maintain adequate documentation of timely event reporting. Delegated study personnel are to enter the UADE information into the EDC system. This will prompt an automatic email confirmation of the UADE data entry to Galil Medical personnel.

It is the responsibility of the investigator to inform the Institutional Review Board (IRB)/Independent Ethics Committee (IEC) of SAEs/UADEs as required by local procedure. Galil Medical is responsible for relaying adequate information on SAEs/UADEs to all investigators participating in this study as well as to the FDA and other regulatory authorities.

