15.3. Institutional Review Board/Independent Ethics Committee

This protocol, the Informed Consent Form (ICF) and relevant supporting information must be submitted to an IRB/IEC before a site is initiated for participation. Approval from the IRB/IEC must be obtained before any study assessments are performed. IRB/IEC approval shall be documented in a letter to the investigator, clearly identifying this protocol, the documents reviewed and the date of approval. This protocol will be conducted in accordance with applicable local regulatory and IRB/IEC requirements.

The investigator is responsible for keeping his/her local IRB/IEC apprised of the progress of the study and of any protocol changes, as necessary. Galil Medical will be responsible for updating the study's central IRB/IEC, if applicable.

Investigators are required to notify their local IRB/IEC of all Serious Adverse Events (SAEs) and all Unexpected Adverse Device Events (UADEs). Investigators under the jurisdiction of the study's central IRB/IEC are required to promptly notify Galil Medical of such events so that Galil Medical can notify the central IRB/IEC.

The investigator will be responsible for obtaining annual IRB/IEC approval and renewal throughout the duration of the study.

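### Section 13 requires adverse-event recording only to day 30, which conflicts with the UADE rule in 13.3, and the safety endpoint states no period

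*Protocol*

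**What the plan says.** **Recording window.** The opening paragraph of Protocol Section 13 says that AEs, SAEs and UADEs "that occur within 30 days after the cryoablation procedure is performed will be recorded". Its second sentence says that those "identified within the first 30 days after the cryoablation procedure will be followed and reported until resolution".

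**Rules without a time limit.**
- Section 13.1: "All AEs must be recorded in the electronic database".
- Section 13.3, SAEs: "Any SAE must be reported by the investigator", within 24 hours of learning of the event.
- Section 13.3, UADEs: investigators must submit "a report of any UADE occurring during an investigation as soon as possible", and site staff must enter the UADE in the EDC system.
- Section 15.3: "Investigators are required to notify their local IRB/IEC of all Serious Adverse Events (SAEs) and all Unexpected Adverse Device Events (UADEs".

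**Visits.** Table 1 and Sections 7.6 and 7.7 list a safety assessment at months 3, 6, 12, 18 and 24, in addition to the procedure, week 1 and month 1.

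**Endpoint.** Protocol 5.2 and 10.5.4 and the SAP's Safety Endpoint Analysis call for the incidence and severity of cryoablation-related events, with point estimates and two-sided 95% confidence intervals. Protocol 10.5.4 and the SAP place SAEs and UADEs inside that endpoint. None of these sections names an onset period.

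**Risks.** Section 5.7: "Potential delayed risks of pulmonary tumor cryoablation include pneumothorax, pulmonary embolus, infection, and other unlikely complications, including death". It does not say how late is meant.

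**The concern.** Safety is half of the study objective, and its result will be an incidence with a confidence interval. Such a figure needs a stated period and a capture rule that all sites apply alike. Here the section governing capture stops its requirement at day 30, other sections carry no limit, and visits with a safety assessment continue to month 24.

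Two things are at stake. First, an SAE or UADE at month 4, reported under 13.3, may or may not enter the reported rate; the analyst has no rule. Second, a non-serious related event that starts after day 30 need not be recorded at all, so sites may differ in what they enter. A reader of the results could take the rate as covering the 24 months of follow-up when required capture covers 30 days.

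**Working it through.** The documents give no figure to reproduce on this point. The check is a comparison of passages with some day arithmetic.

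**1. Rules side by side, for an event starting at month 4**

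| Event | Section 13 opening | Other sections | Result |
|---|---|---|---|
| UADE | Recording not required | 13.3: report and EDC entry for any UADE during the investigation; 15.3: notify the IRB/IEC | Firm conflict: an investigation with 24-month follow-up cannot be read as 30 days |
| SAE | Recording not required | 13.3: any SAE to the sponsor; 15.3: all SAEs to the IRB/IEC | Conflict on its face; could be read as subject to Section 13, or as notification only |
| Non-serious related AE | Recording not required | 13.1: all AEs, no limit stated | No firm conflict; Section 13 may govern its own subsection |

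**2. Visits beyond the window**
- Month 3, taken as day 90, has a window of ±30 days, so the earliest visit is 90 − 30 = day 60.
- Months 3, 6, 12, 18 and 24 therefore all fall after day 30. That is 5 of the 7 post-procedure safety assessments.
- As a share of follow-up: 24 × 30.4375 = 730.5 days, and 30 / 730.5 = 4.1%.

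**3. Occurrence against identification**
- The month 1 window is 30 − 7 = day 23 to 30 + 21 = day 51.
- An AE that starts on day 28 and is found at a day-45 visit is recorded under the first sentence of Section 13. It falls outside the second sentence, because it was not identified within 30 days, so the duty to follow it to resolution does not reach it.

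**4. Which procedure starts the clock**
- Section 13 speaks of one procedure. Table 1 allows staged treatment over 8 weeks = 56 days, and Section 7.8 allows repeat treatment.
- Section 7.10 follows medications to 30 days after the last procedure. Table 1 footnote h ties visit windows to the most recent procedure, and 7.8 restarts visits after retreatment. These point to each or the last procedure, but Section 13 does not say so.
- With sessions on days 0 and 56, an each-procedure clock covers days 0–30 and 56–86, and a last-procedure clock covers days 0–86. They differ for onsets on days 31–55, which is 25 days.

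**5. Scale**
- The documents give no rate of related events starting after day 30, so the effect on the safety estimate cannot be computed.
- As a unit only: if incidence is counted per patient over the planned 150, each patient whose sole related event starts after day 30 and goes unrecorded lowers it by 1/150 = 0.67 percentage points.

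**The case against.** The strongest defence has five parts.

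- **Structure.** The 30-day paragraph opens Section 13, so 13.1 and 13.3 can be read under it. Section 15.3 and the SAE sentence in 13.3 concern notification, whose scope may differ from recording. This stands for non-serious AEs and is arguable for SAEs. It fails for UADEs, where 13.3 names the investigation as the period and requires database entry.
- **No prohibition.** Section 13 says what will be recorded and does not bar recording later events. This stands. A reader might infer that nothing starting after day 30 is recorded at months 3 to 24, or that the trial could say nothing about late events. The documents support only that such recording is not required.
- **Deliberate design.** Section 7.10 uses the same 30 days for medications, and 10.5.4 speaks of intra-operative and post-operative events. A 30-day window for all AEs is defensible, and the later visits may serve to follow early events to resolution. This stands, but does not supply the missing period.
- **Other safeguards.** Section 16.1 provides a Medical Monitor for the whole study, and deaths enter overall survival and subject disposition. These help oversight. They do not decide what enters the related-event rate, and the death tallies carry no attribution.
- **No evidence of late events.** Section 5.7 does not date its delayed risks. A cryoablation series cited in Section 3.2 reports delayed pneumothorax in 30 of 193 sessions, also undated. A reader might infer that the safety rate is materially understated; nothing in the documents shows a related event with onset after day 30.

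**Conclusion.** The point holds as an inconsistency and an undefined endpoint period. The UADE conflict between Section 13 and 13.3 is firm. The SAE conflict with 13.3 and 15.3 exists on the face of the text but admits a reconciling reading. For non-serious AEs the 30-day window is a design choice and not a contradiction.

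The consequence is that the SAP has no rule for counting a late SAE or UADE, and that related events with onset after day 30 lie outside required capture at five scheduled assessments. It would be wrong to go on from the SAE and UADE conflict to say that serious events are lost: if 13.3 and 15.3 are followed, they are still reported, and the events most exposed are non-serious ones.

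The size is unknown. The 0.67-point unit assumes a per-patient rate over 150 patients and measures no bias. Safety carries no hypothesis test, and the primary efficacy test is unaffected. The change should be made because it is cheap and settles what the safety rate means.

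**What to change.** **Protocol**
- Reconcile Section 13 with 13.1, 13.3 and 15.3.
- Keep the 30-day window for all AEs. With later onset, record SAEs, UADEs and AEs judged related or possibly related to the procedure or device, at the safety visits already scheduled.
- Make both sentences of Section 13 go by onset, and state the clock for staged and repeat procedures.

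**SAP**
- Label the related-event incidence and its 95% confidence interval as onset within 30 days. Section 13.1 already asks for the start date ("A description of the event, including the start date, resolution date, action taken and the outcome should be provided"), and 13.2 already asks for causality, so the cut needs no new field.
- List later related events, SAEs and UADEs separately as counts, with the number of patients under observation. Do not pool them into a 24-month rate.
- Note incomplete capture for patients already past those visits. The SAP revision entry of January 2017 shows that patients were already in the study, so their later events may be only partly recoverable.

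**Cost.** Wording in two documents, plus a modest number of extra AE forms and causality assessments, some for disease-related SAEs. No new visits or forms are needed. Stating the period in the SAP needs no new data and can be done even if late capture stays incomplete.

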13.1. List of Definitions

Adverse Event (AE)

Any untoward or unfavorable medical occurrence in a human patient, including any abnormal sign (for example, abnormal physical exam or laboratory finding), symptom, or disease, temporally associated with the patient's participation in the research, whether or not considered related to the patient's participation in the research. All AEs must be recorded in the electronic database. A description of the event, including the start date, resolution date, action taken and the outcome should be provided, along with the investigator's assessment of the relationship between the AE and the study procedures.

The anticipated cryoablation related adverse events and their corresponding Common Terminology Criteria for Adverse Events (CTCAE) Terms are listed in Appendix B.⁴³

Serious Adverse Event (SAE)

Category 4 or higher of the CTCAE guidelines and the following ICH definitions will be used in the protocol as applicable.

- Results in Death

- Is Life Threatening

Note: The term 'life threatening' in the definition of serious refers to an event in which a patient was at immediate risk of death at the time of the event; it does not refer to an event which hypothetically might have caused death if it were more severe.

- Requires inpatient hospitalization or prolonged existing hospitalization

Note: Complications that occur during hospitalization are AEs. If a complication prolongs hospitalization or fulfills any other serious criteria, the event is serious. Hospitalization for elective treatment of a pre-existing condition that did not worsen from baseline is not considered to be an AE.

- Results in persistent or significant disability/incapacity

Note: The term disability means a substantial disruption of a person's ability to conduct normal life functions. This definition is not intended to include experiences of relatively minor medical significance (e.g., uncomplicated headache, nausea, vomiting, diarrhea, influenza, or accidental trauma) that may interfere or prevent everyday life functions, but do not constitute a substantial disruption.

- Results in permanent impairment of a body structure or body function or requires surgical intervention to prevent permanent impairment of a body structure or body function

- Leads to fetal distress, fetal death or a congenital anomaly/birth defect

- Important medical events that may not be immediately life threatening, or result in death or hospitalization but may jeopardize the patient or may require intervention to prevent one of the outcomes listed in the definition above should also usually be considered serious.

Note: Examples of such events are intensive treatment in an emergency room or at home for allergic bronchospasm, blood dyscrasias, or convulsions that do not result in hospitalization; or development of drug dependency or drug abuse.

Unanticipated Adverse Device Effect (UADE)

Unanticipated adverse device effect is any serious adverse effect on health or safety, any life-threatening problem or death caused by, or associated with a device, if that effect, problem, or death was not previously identified in nature, severity, or degree of incidence in the application; or any other unanticipated serious problem associated with a device that relates to the rights, safety, or welfare of patients.

13.2. Causality Assessment

The investigator's assessment of causality must be provided for all adverse events (serious and non-serious). An investigator's causality assessment is the determination of whether there exists a reasonable possibility that the procedure and/or study device caused or contributed to an adverse event. If the investigator's final determination of causality is unknown and the investigator does not

know whether or not the procedure and/or study device caused the event, then the event will be handled as “related to procedure or study device” for reporting purposes. If the investigator’s causality assessment is “unknown but not related to procedure or study device,” this should be clearly documented on study records.

The investigator will evaluate AEs/SAEs/UADEs using the following guidelines:

- Description of event (if the event consists of multiple signs and symptoms, a diagnosis should be recorded rather than each sign and symptom)
 - Record term and grade according to the CTCAE 4.03 grading criteria
- Onset date
- Stop date
- Seriousness
 - The investigator must determine whether or not the AE meets the definition of serious as noted above and record in the eCRF. If the event is serious, the investigator must inform the Sponsor within 24 hours of knowledge of the event and complete the SAE report form.
- Relationship to Study Procedure and/or Study Device
 - The investigator must make a causality assessment for all AEs and decide whether there is a reasonable possibility the AE was caused by the procedure and/or study device.
 - If there is a valid reason to suspect a causal relationship between the AE and the procedure and/or study device, the AE should be considered “related or possibly related” to the procedure or study device.
- Outcome
- Action Taken

